7.4.5 Subgroup analyses

Subgroup analyses will be performed as post-hoc analyses to determine if all subgroups experience similar treatment effects or if there are subgroups that behaved differently. The methods will be determined based on:

- Pre-specify subgroups that will be analyzed. Consider subgroups defined by:
 - Baseline values of outcome variables
 - Different types of baseline disease status (e.g., prior atrial fibrillation history)
 - Different levels of key prior exposures (e.g., smoking status/exposure, atrial fibrillation status at discharge)
- Pre-specify how the results will be interpreted:
 - We expect to see that the effects of risk factors will be in the same direction with different intensities. If we are able to identify certain subgroups that are significantly different from others, we will report the results with suggestions for future studies.

7.5 Post-hoc (data driven) analyses:

Post-hoc data driven analyses are allowed after the following are undertaken.

- (a) Document which analyses were conducted after the results for the Primary and Secondary Aims are analyzed.
- (b) Document the rationale for these analyses.
- (c) Pre-specify their interpretation in the context of the primary and secondary results and their impact on the overall trial conclusions.

7.6 Sensitivity Analyses

The negative control outcome analysis mentioned in section 3.4 will be part of the sensitivity analyses, which evaluates whether there is unmeasured confounding effect in the prior AF-postoperative AF association. A similar analysis will be performed for stroke, and all-cause mortality. Additionally, we will report E-values for the associations from these models. The E-value is defined as the minimum strength of association, that an unmeasured confounder would need to have with both the exposure and the outcome to fully explain away a specific exposure-outcome association, conditional on the measured covariates

When patient characteristics are significantly different between the prior AF group and non-prior AF group, stratified proportional hazard models with two sets of coefficients will be fitted, and the effects of risk factors will be evaluated. Consistency of the two sets of coefficients would reflect the imbalance of baseline variables is negligible, and one final model will be reported. For the analysis of recurrent data, consistency of the results from AG and PWP models will be monitored.

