1.2 Background Literature

Atrial fibrillation (AF) is the most common cardiac arrhythmia and frequently presents in association with mitral, other valvular and coronary artery disease, notably in the presence of poorer left ventricular function (1,2). Preoperative AF is reported commonly in patients undergoing cardiac surgery, with an incidence of 10-20% (2-8). Even if treated, preoperative AF is associated with a higher incidence of in-hospital postoperative AF, stroke, other cardiac morbidity and mortality (2,6,9-11).

Conventional management of postoperative AF assumes that it results from self-limited causes, such as postoperative pericarditis, surgical stress, and sympathetic stimulation in patients underlying heart disease that can be treated with short-term antiarrhythmics, heart rate reduction, anti-coagulants and anti-platelet agents. However, it is well-known that AF in the immediate postoperative period is associated with increased risk of post-discharge AF and stroke. Observed incidences range widely (3-25%) depending principally on the duration of follow-up and the mode of monitoring (12-14). These studies did not use continuous ECG monitoring to detect AF recurrence, and therefore may have underestimated the incidence of AF by missing asymptomatic AF. Using continuous ECG monitoring the incidence of at least one electrocardiographic episode of AF lasting longer than six minutes is much higher; 60% over the entire follow-up period and 39% occurring more than 3-months after surgery (15).

Thromboembolic stroke is a major preventable cause of morbidity and mortality in patients with post-operative AF (16-18). Studies have demonstrated a risk-unadjusted two to ten-fold increase in embolic events and a threefold increased risk of cardiac death in patients with postoperative AF (12,19,20).

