4 ESTIMATION OF ACCESSIBLE EFFECT SIZE

This will be a retrospective cohort study. Patients will be included in the study based on the inclusion and exclusion criteria. All statistical tests will be two-sided and the statistical significance level will be set at 0.05 unless otherwise stated. Assuming 50,000 patients will be included in the analysis, among which 4000 (8%) have prior AF, we will have 80% power to detect a Cohen's effect size of 0.046 at the 0.05 significance level. If 25% of the patients who do not have prior AF have postoperative AF, a Cohen's effect size of 0.046 is corresponding to a 2% difference in the incidence of postoperative AF.

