7.4 Statistical Analytical Issues

7.4.1 Adjustments for covariates

There will be covariate adjustment in the primary analysis.

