7.4.3 Examination of Subgroups

To determine if all subgroups experience similar treatment effects or if there are subgroups that behaved differently. We will report odds ratios with 99% confidence intervals for the primary outcome by the following subgroups, with/without prior atrial fibrillation before surgery, and with/without atrial fibrillation when discharged. We will conduct a test of homogeneity of effects across the subgroups and report a P value. Unless there is strong evidence against the null hypothesis of homogeneity of effects (i.e. $p<0.001$) the overall odds ratios will be considered as the most reliable guide to the approximate relative risks in all subgroups.

7.4.4 Correlated data, bias, confounding and interactions.

Collinearity between risk factors will be evaluated with Variance Inflation Factors (VIF) or generalized VIF. Risk factors with high VIF (>2.5) will be excluded in the models.

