Descriptive data	14*	
(a) Give characteristics of study participants (eg demographic, clinical, social) and information on exposures and potential confounders
 
(b) Indicate number of participants with missing data for each variable of interest
 
(c) Summarise follow-up time (eg, average and total amount)

Outcome data	15*	Report numbers of outcome events or summary measures over time
Main results	16	
(a) Give unadjusted estimates and, if applicable, confounder-adjusted estimates and their precision (eg, 95% confidence interval). Make clear which confounders were adjusted for and why they were included
 
(b) Report category boundaries when continuous variables were categorized
 
(c) If relevant, consider translating estimates of relative risk into absolute risk for a meaningful time period

Other analyses	17	Report other analyses done—eg analyses of subgroups and interactions, and sensitivity analyses
Discussion		
Key results	18	Summarise key results with reference to study objectives
Limitations	19	Discuss limitations of the study, taking into account sources of potential bias or imprecision. Discuss both direction and magnitude of any potential bias
Interpretation	20	Give a cautious overall interpretation of results considering objectives, limitations, multiplicity of analyses, results from similar studies, and other relevant evidence
Generalisability	21	Discuss the generalisability (external validity) of the study results
Other information		
Funding	22	Give the source of funding and the role of the funders for the present study and, if applicable, for the original study on which the present article is based

*Give information separately for exposed and unexposed groups.

Note: An Explanation and Elaboration article discusses each checklist item and gives methodological background and published examples of transparent reporting. The STROBE checklist is best used in conjunction with this article (freely available on the Web sites of PLoS Medicine at <http://www.plosmedicine.org/>, Annals of Internal Medicine at <http://www.annals.org/>, and Epidemiology at <http://www.epidem.com/>). Information on the STROBE Initiative is available at <http://www.strobe-statement.org>.

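### Section 7.6 reads agreement of the coefficients fitted by prior-AF group as negligible baseline imbalance; agreement shows only that no interaction with prior AF was detected

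*Combined protocol and SAP*

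**What the plan says.** The second paragraph of Section 7.6 sets a trigger and a conclusion. The trigger is a significant difference already found: "When patient characteristics are significantly different between the prior AF group and non-prior AF group, stratified proportional hazard models with two sets of coefficients" are then to be fitted and the risk-factor effects examined. The conclusion is: "Consistency of the two sets of coefficients would reflect the imbalance of baseline variables is negligible, and one final model will be reported".

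Four other places bear on how this should be read:

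- Section 7.4.1: "There will be covariate adjustment in the primary analysis". Section 2.3 names preoperative AF as the main risk factor in both primary aims, and Section 7.1.1 analyses both with Cox models.
- Section 7.4.3 compares effects across subgroups that include prior AF, and describes this as a question of homogeneity: "Unless there is strong evidence against the null hypothesis of homogeneity of effects", the overall odds ratio is to stand.
- Section 7.4.5 lists prior-AF history as a possible subgroup and says what happens when effects differ: "If we are able to identify certain subgroups that are significantly different from others, we will report the results with suggestions for future studies".
- The STROBE checklist in Section 13, item 16(a), asks authors to do the following: "Give unadjusted estimates and, if applicable, confounder-adjusted estimates and their precision".

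**The concern.** Imbalance is a difference between the two groups in the distribution of baseline characteristics. The two coefficient sets estimate something else: how each characteristic relates to the outcome within each group. Agreement of the second does not tell the reader the size of the first. The sentence also sits badly with its own trigger, because the models are fitted only after the groups have been found to differ.

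What is at stake is a statement in the report. If the section is followed literally, the authors could write that measured differences between the prior-AF groups are negligible, on evidence that cannot show it.

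**Working it through.** **The plan's own figure.** Section 4 assumes 50,000 patients, 4,000 of them with prior AF (so 46,000 without), two-sided 0.05 and 80% power. The detectable effect is h = (1.960 + 0.842) × √(1/4000 + 1/46000) = 2.802 × 0.01648 = 0.0462. The plan gives 0.046. By the arcsine transform, 0.046 takes 25% to 27.0%, the stated 2-point difference. The figure reproduces. The present point does not depend on it, but the group sizes are used below.

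**Inputs.** From Section 4: 4,000 and 46,000 patients, and 25% events without prior AF ("If 25% of the patients who do not have prior AF have postoperative AF"). From Section 1.2: 3% as a low event rate ("Observed incidences range widely (3-25%) depending principally on the duration of follow-up and the mode of monitoring"). My assumptions, not in the documents: one binary covariate with prevalence 30% without prior AF and 30%, 45% or 60% with it; the covariate hazard ratios (HRs) shown; a prior-AF HR of 1 when the covariate is absent; exponential event times; censoring uniform over 1 to 6 years; 300 simulated cohorts per scenario.

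**1. How easily the trigger is met.** At p<0.05 the groups differ significantly once the gap reaches 1.96 × 0.01648 = 0.032 SD. For a characteristic with 30% prevalence that is 0.0323 × √(0.3 × 0.7) = 0.0148, or 1.5 percentage points. Even with perfect balance, the chance that at least one of K independent characteristics reaches p<0.05 is 1 − 0.95^K: 40%, 64% and 87% for K = 10, 20 and 40. The branch will almost certainly be entered. That is not a fault in itself, but it means the clause is likely to be used.

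**2. Imbalance without interaction.** Covariate HR 2.0 in both groups, 25% events. The expected crude prior-AF HR at the start of follow-up is [1 + p₁(2 − 1)] / [1 + p₀(2 − 1)], where p₁ and p₀ are the prevalences with and without prior AF.

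| Prevalence with prior AF | 30% | 45% | 60% |
|---|---|---|---|
| Ratio of the two covariate HRs | 0.999 | 0.999 | 1.004 |
| 5% test of equal coefficients rejects | 3.3% | 4.7% | 5.7% |
| Crude prior-AF HR, formula | 1.30/1.30 = 1.000 | 1.45/1.30 = 1.115 | 1.60/1.30 = 1.231 |
| Crude prior-AF HR, simulated | 0.999 | 1.114 | 1.232 |
| Adjusted prior-AF HR, simulated | 0.998 | 1.001 | 1.001 |

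The coefficients agree in every column, so agreement does not track imbalance. The last row shows what agreement does support: one adjusted model is adequate.

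**3. Interaction without imbalance.** Prevalence 30% in both groups, covariate HR 1.5 without and 2.0 with prior AF. The standard error of the log ratio is 0.064, so z = ln(2.0/1.5)/0.064 = 0.288/0.064 = 4.50 and power at 5% is Φ(4.50 − 1.96) = 99.4%. The simulation gives 99.3%. The coefficients disagree although balance is perfect, so disagreement does not indicate imbalance either.

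**4. Strength of agreement for a rarer endpoint.** At 3% events the standard error is 0.182, so z = 0.288/0.182 = 1.58 and power is Φ(1.58 − 1.96) = 35%. The simulation gives 34.3%, 37.0% and 34.7% at the three prevalences. Agreement then means that interaction was not detected, which is less than showing it absent.

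**5. Cross-check with a continuous covariate.** Assumed log HR 0.5 per SD, prior-AF HR 1.5, about 21% events, one run each. With a 1.0 SD imbalance the group coefficients were 0.517 and 0.520 (p = 0.94); with no imbalance, 0.517 and 0.515 (p = 0.94). With the 1.0 SD imbalance the prior-AF HR was 2.45 crude and 1.53 adjusted. With no imbalance but a real interaction, the coefficients were 0.517 and 0.227 (p<0.001).

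**The case against.** The strongest reply is that the paragraph is about which model to report. Since covariate adjustment is planned, negligible may mean negligible for the single adjusted model. Step 2 supports that practical use, and this part of the objection stands. The sentence, however, attributes negligibility to the imbalance itself, and a report repeating it would be read that way.

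Several stronger readings are tempting, and the documents do not support them:

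- A reader might infer that the primary prior-AF hazard ratio is biased, or that consistency lets the authors drop adjustment or the prior-AF term. Sections 2.3, 7.1.1 and 7.4.1 keep all of these, and nothing in 7.6 removes them. Separate fits by prior AF give no prior-AF hazard ratio, but the primary model supplies it.
- A reader might infer that the plan says nothing about coefficients that differ. Section 7.4.5 already covers reporting when effects differ by prior-AF history; 7.6 only lacks the cross-reference.
- A reader might expect the published tables to contradict the text. No shell table is laid out by prior AF: Table 1 describes all participants, and Table 2 compares patients with and without post-discharge AF.
- A reader might ask for a formal threshold for consistency. I do not. The p<0.001 rule in 7.4.3 is written for odds ratios. As one global test it would detect the 1.5 versus 2.0 difference in a single covariate with power of about 49%, 30% and 15% for 10, 20 and 40 covariates at 25% events, and under 1% at 3% events.
- When interaction is present, the single-model prior-AF hazard ratio becomes an average of a varying effect. That is effect modification, not harm done by the rule in 7.6.

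**Conclusion.** Wrong as written; minor. Agreement of the two coefficient sets supports one covariate-adjusted model for the measured covariates, and nothing about the size of the imbalance. In the binary example, imbalance that moved the crude prior-AF hazard ratio from 1.00 to 1.23 left the coefficient comparison unchanged and the adjusted hazard ratio at 1.00. Those magnitudes depend on the assumed covariate. The logic does not, because the coefficients are estimated within groups and do not estimate the difference between the groups' distributions. With a misspecified functional form, imbalance could also make the coefficients differ, but agreement would still not measure it. The effect is on how a sensitivity analysis is described, not on the primary estimate.

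**What to change.** Change the paragraph in Section 7.6 as follows.

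1. Replace the clause on negligible imbalance with wording such as: *Consistency indicates that no interaction between the covariates and prior AF was detected, and so supports reporting one covariate-adjusted model.*
2. State that the primary adjusted Cox model, with its prior-AF term, is reported in either case. When the coefficients differ, show the group-specific coefficients alongside it, and cross-reference Section 7.4.5.
3. Judge the influence of measured imbalance from crude and adjusted prior-AF hazard ratios shown side by side, as STROBE item 16(a) in Section 13 already asks.

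The cost is a few sentences and one column of crude hazard ratios. The gap between crude and adjusted values reflects measured covariates only. It also contains slight non-collapsibility: in balanced scenarios with a prior-AF hazard ratio of 1.5, the crude-to-adjusted ratio was 0.997, 0.991 and 0.977 for covariate hazard ratios of 1.5, 2.0 and 3.0. A footnote to the table can say both.

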8 APPENDIX: STUDY ADMINISTRATION

8.1 Confidentiality

Data will be stored on encrypted hard drives and backed up to secure Partners-maintained storage within the Partners firewall. Secure transfer methods will be used. Final results will be reported in aggregate with no individually identifying data.

Linkage is done on a stand-alone PC which is not used by the analysts. The linkage process uses only temporary data sets that are immediately removed once the program has completed. The final analytic data set does not contain any patient names, addresses, or social security numbers. It also does not contain any CHIA case mix data fields.

8.2 Records Retention

We anticipate follow-on studies in the field that can be performed with this data set. Therefore, records will be retained for up to five years for follow-on studies, provided each site agrees to this plan.

8.3 Informed Consent/Assent and HIPAA Authorization

Waiver of informed consent has been granted for this retrospective chart review study as it meets the following criteria pursuant to 45 CFR 46.116(d):

- The research involves no more than minimal risk to the subjects.
- The waiver or alteration will not adversely affect the rights and welfare of the subjects.
- The research could not practicably be carried out without the waiver or alteration.

Waiver of HIPAA authorization has been granted as it meets the following criteria pursuant to 45 CFR 164.512(i)(1)(i)

- The use or disclosure of protected health information involves no more than a minimal risk to the privacy of individuals, based on, at least, the presence of the following elements:
 - an adequate plan to protect the identifiers from improper use and disclosure;
 - an adequate plan to destroy the identifiers at the earliest opportunity consistent with conduct of the research, unless there is a health or research justification for retaining the identifiers or such retention is otherwise required by law; and
 - adequate written assurances that the protected health information will not be reused or disclosed to any other person or entity, except as required by law, for authorized oversight of the research project, or for other research for which the use or disclosure of protected health information would be permitted by this subpart;
- The research could not practicably be conducted without the waiver or alteration; and
- The research could not practicably be conducted without access to and use of the protected health information.

9 APPENDIX: DATA TO BE OBTAINED FROM MASSACHUSETTS CARDIAC SURGICAL PROGRAMS

Line				STS 2.81	STS 2.73	STS 2.61	STS 2.52
number	Section	Variable text	STS variable names	numbers	numbers	numbers	numbers
1		STS database version					
2	B. Demographics						
3		Patient Last Name	PatLName	50	90	100	100
4		Patient First Name	PatFName	55	100	110	110
5		Zip Code	PatZip	105	210	180	180
6		Medical Record Number	MedRecN	85	170	170	170
7		Date of Birth	DOB	65	130	130	130
8		Gender	Gender	75	150	150	150
9		Race	Race	-	-	190	190
10		Race	RaceDocumented	150	-	-	-
11		RaceCaucasian	RaceCaucasian	155	290	191	-
12		RaceBlack	RaceBlack	160	300	192	-
13		RaceAsian	RaceAsian	165	310	193	-
14		RaceNativeAm	RaceNativeAm	170	320	194	-
15		RaceNativePacific	RaceNativePacific	175	330	195	-
16		RaceOther	RaceOther	180	340	196	-
17		Ethnicity	Ethnicity	185	350	199	-
18	C. Hospitalization						
19		Hospital Name	HospName	205	380	220	220
20		Date of Surgery	SurgDt	310	610	260	260
21		Date of Discharge	DischDt	315	620	270	270
22		Payor	PayorGov	225	420	247	-
23		Payor	PayorComm	275	510	254	-
24		Payor	PayorHMO	280	520	255	-
25	D. Risk Factors						
26		Height	HeightCm	330	640	360	360
27		Weight	WeightKg	335	630	350	350
28		Diabetes	Diabetes	360	780	400	400

29	Diabetes - control	DiabCtrl	365	790	410	410
30	Dyslipidemia	Dyslip	370	800	420	420
31	Dialysis	Dialysis	375	810	450	450
32	Hypertension	Hypertn	380	820	460	460
33	Smoker	TobaccoUse	400	-	-	-
34	Smoker	CigSmoker	-	650	370	370
35	Smoker	SmokCurr	-	660	-	-
36	Chronic Lung Disease	ChrLungD	405	860	510	510
37	Sleep Apnea	SlpApn	460	950	-	-
38	Alcohol Use	Alcohol	480	1131	-	-
	Peripheral Artery					
39	Disease	PVD	505	980	530	530
40	Cerebrovascular disease	CVD	525	1010	540	540
41	Prior CVA	CVA	530	1020	470	470
42	Prior CVA-When	CVAWhen	535	1030	480	480
43	CVD TIA	CVDTIA	540	1050	540	540
44	CVD Carotid stenosis	CVDCarSten	545	1070	550	550
45	Right carotid disease	CVDStenRT	550	1071	-	-
46	Left carotid disease	CVDStenLft	555	1072	-	-
47	Priot carotid surgery	CVDPCarSurg	560	1080	-	-
48	WBC Count	WBC	565	690	-	-
49	Last Creatinine	CreatLst	585	750	430	430
50	Infectious endocarditis	InfEndo	385	830	490	490
51	E. Previous Cardiac Interventions					
	Previous Cardiac					
52	Interventions	PrCVInt	665	1200	570	570
53	Previous CABG	PrCAB	670	1215	600	600
54	Previous Valve	PrValve	675	1216	610	610
	Previous valve surgery					
55	type 1	PrValveProc1	695	-	-	-
	Previous valve surgery					
56	type 2	PrValveProc2	700	-	-	-
	Other Previous Cardiac					
57	Interventions	POC	805	-	620	620

	Other previous cardiac					
58	intervention 1	POCInt1	810	-	-	-
	Other previous cardiac					
59	intervention 2	POCInt2	815	-	-	-
	Other previous cardiac					
60	intervention 3	POCInt3	820	-	-	-
	Previous carotid artery					
61	surgery	CVDPCarSurg (1080)	-	1080	557	557
62	Previous ICD	PrOCAICD	-	1460	630	630
63	Previous Pacemaker	PrOCPace	-	1470	640	640
	Previous arrhythmia					
64	surgery	POArr	-	1445	-	-
65	Previous other cardiac	PrOthCar	-	1440	-	-
66	Previous congenital	PrOthCongen	-	1450	621	-
	Previous Aortic Valve					
67	Replacement - Surgical	PrevProcAVReplace	-	1220	-	-
	Previous Aortic Valve					
68	Repair - Surgical	PrevProcAVRepair	-	1230	-	-
	Previous Mitral Valve					
69	Replacement - Surgical	PrevProcMVReplace	-	1240	-	-
	Previous Mitral Valve					
70	Repair - Surgical	PrevProcMVRepair	-	1250	-	-
	Previous Tricuspid Valve					
71	Replacement - Surgical	PrevProcTVReplace	-	1260	-	-
	Previous Tricuspid Valve					
72	Repair - Surgical	PrevProcTVRepair	-	1270	-	-
	Previous Pulmonic Valve					
	Repair / Replacement -					
73	Surgical	PrevProcPV	-	1280	-	-
	Previous Aortic Valve					
74	Balloon Valvuloplasty	PrevProcAVBall	-	1285	-	-
	Previous Mitral Valve					
75	Balloon Valvuloplasty	PrevProcMVBall	-	1290	-	-
76	Previous Transcatheter	PrevProcTCVRep	-	1300	-	-

		Valve Replacement				
		Previous Percutaneous	PrevProc	PercVR	Repai	
77	Valve Repair	r	-	1310	-	-
F. Preoperative Cardiac Status						
79	Previous MI	PrevMI	885	1540	750	750
80	Previous MI - when	MIWhen	890	1550	760	760
81	Prior Heart Failure	PriorHF	920	1590	770	770
82	History of Arrhythmia	Arrhythmia	945	-	840	840
83	History of Arrhythmia	ArrhythWhen	-	1650	-	-
84	VT/VF	ArrhyVtach	-	1660	851	-
		ArrhyVtachSicSinSyn				
85	Sick sinus syndrome	;	-	1680	-	-
86	Third degree heart block	ArrhyTHB	-	1690	852	-
	Second degree heart					
87	block	ArrhyVtachHrtBlk	-	1670	-	-
88	VT/VF	ArrhythVV	950	-	-	-
89	Sick sinus syndrome	ArrhythSSS	955	-	-	-
90	Atrial Flutter	ArrhythAFlutter	960	-	-	-
	Second degree heart					
91	block	ArrhythSecond	965	-	-	-
92	Third degree heart block	ArrhythThird	970	-	-	-
93	Paced rhythm	ArrhythPPaced	975	-	-	-
94	Afib/Aflutter	ArrhythAFib	980	1700	853	-
95	Type of Atrial Fibrillation	ArrhyTyp	-	-	850	850
	Duration of Atrial					
96	Fibrillation	ArrythAFibDur	985	-	-	-
97	Type of Atrial Fibrillation	ArrythAFibTy	-	1701	-	-
G. Preoperative Medications						
99	ACE inhibitor Use	MedACEI48	1020	1730	900	900
100	Anticoagulant Use	MedACoag	1040	1750	940	940
101	Amiodarone Use	MedAmiodarone	1035	-	-	-
102	Aspirin Use	MedASA	1055	1820	990	990
103	B-blockers <24 hours	MedBeta	1060	1710	890	890
104	B-blockers >2 weeks	MedBetaTher	1065	-	-	-

Calcium Channel						
105	Blocker	MedCChanTher	1070	-	-	-
	Preoperative					
106	Antiarrhythmics	MedAArrhy	-	1770	-	-
107	Coumadin	MedCoum	1075	1780	950	950
108	H. Hemodynamics Cath					
	Number of Diseased					
109	Vessels	NumDisV	1170	1930	1050	1050
110	LV ejection fraction	HDEF	1545	1960	1080	1080
111	Aortic Insufficiency	VDInsufA	1590	2155	1170	1170
112	Aortic Stenosis	VDStenA	1600	2152	1120	1120
113	Aortic Valve Area	VDAoVA	1610	2153	-	-
	Aortic Valve Mean					
114	Gradient	VDGradA	1615	2154	1130	1130
115	Mitral Insufficiency	VDInsufM	1680	2270	1180	1180
116	Mitral Stenosis	VDStenM	1690	2240	1140	1140
	Mitral Valve Mean					
117	Gradient	VDGradM	1705	2260	1180	1180
118	Tricuspid Insufficiency	VDInsufT	1775	2320	1190	1190
119	Tricuspid Stenosis	VDStenT	1785	2300	1150	1150
120	Pulmonary Insufficiency	VDInsufP	1820	2340	1200	1200
121	Pulmonary Stenosis	VDStenP	1840	2330	1160	1160
122	I. Operative (with sections J, K, L and M)					
123	AF procedure	AFibProc	2145	-	2470	2470
124	Afib epicardial lesions	OCarAFibEpLes	4070	-	-	-
125	Afib intracardiac lesions	OCarAFibIntraLes	4105	-	-	-
126	Aortic Arch	AortProcTotArch	4355	-	-	-
127	Aortic Arch	ONCArch	-	-	2530	2530
128	Aortic Arch	ONCArch	-	5480	-	-
129	Aortic Hemi-arch	AortProcHemi	4350	-	-	-
130	Aortic Procedure	AortProc	2150	-	-	-
131	Aortic Procedure	OpAortic	-	-	1630	1630
132	Aortic Procedure Type	OCAoProcType	-	5471	-	-
133	Aortic Root	AortProcRoot	4340	-	-	-

134	Aortic Root	ONCAoRt	-	5473	-	-
135	Aortic Valve Procedure	VSAVPr	-	4280	-	-
136	Aortic Valve Surgery	VSAV	3390	4270	-	-
	Arrhythmia Correction					
137	Surgery	OCarACD	-	5400	-	-
	Arrhythmia Correction					
138	Surgery Lead Extraction	OCarACDLI	-	5410	-	-
139	Arrythmia device	OCarACD	4085	5400	2450	2450
140	Ascending Aorta	AortProcAsc	4345	-	-	-
141	Ascending Aorta	ONCAsc	-	-	2520	2520
142	Ascending Aorta	ONCAsc	-	5474	-	-
143	ASD-PFO repair	OCarASD		5240	-	-
144	ASD-PFO repair	OCarASDPFO	4075	-	-	-
	Atrial Appendage					
145	Procedure	OCarAAProc	4080	-	2480	2480
	Atrial Fibrillation					
146	Ablation Procedure	OCarAFibAProc	-	5465	-	-
	Atrial Fibrillation Surgical					
147	Procedure	OCarAFibSur	-	5450	-	-
148	CABG performed	OpCAB	2120	2437	1280	1280
149	Cardiac trauma	OCarTrma	4153	5380	2430	2430
150	Cardiac Tumor	OCTumor	4150	5530	-	-
151	Congenital heart surgery	OCarCong	4162	5300	2410	2410
152	Congenital procedure 1	OCarCongProc1	4515	5340	-	-
153	Congenital procedure 2	OCarCongProc2	4520	5350	-	-
154	Congenital procedure 3	OCarCongProc3	4525	5360	-	-
155	CPB time	PerfusTm	2400	2770	1380	1380
156	CPB utilization	CPBCmb	-	2470	1360	1360
157	CPB utilization	CPBUtil	2325	2740	1350	1350
158	Emergency Operation	Status	1975	2390	1240	1240
159	Heart transplant	OCarCrTx	4152	5390	2440	2440
160	Lead extraction	OCarACDLE	4120	-	-	-
161	Lead Insertion	OCarLeadInsert	4090	-	-	-
162	Left Atrial Appendage	OCarAFibSurLAA	-	5452	-	-

	Obliterated					
163	LV aneurysm repair	OCarLVA	4125	5220	2360	2360
164	Mitral Procedure	OpMitral	-	-	1640	1640
165	Mitral Valve Procedure	VSMVPr	-	4352	-	-
166	Mitral Valve Surgery	VSMV	3495	4351	-	-
	Number of anastomoses					
167	with arterial conduits	DistArt	2625	3190	1520	1520
	Number of anastomoses					
168	with venous conduits	DistVein	2630	3220	1530	1530
	Other Cardiac					
169	Procedure	OpOCard	2140	2490	1310	1310
170	Previous VAD	PrevVAD	3790	4760	1920	1920
	Pulmonary					
	thromboendarterectomy					
171	y	OCPulThromDis	4130	5540	-	-
	Pulmonic Valve					
172	Procedure	OpPulm	-	4560	-	-
173	Pulmonic Valve Surgery	VSPV	3685	-	1660	1660
174	Reop surgery	Icidenc	1970	2380	560	560
	Subaortic stenosis					
175	resection	OCarSubaStenRes	4135	-	-	-
	Subaortic stenosis					
176	resection	ResectSubA	-	4311	-	-
	Surgical Procedure					
177	Location	OCarAFibSurLoc	-	5451	-	-
	Surgical ventricular					
178	restoration	OCarSVR	4145	5290	2400	2400
179	TMR	OCarLsr	4100	5370	2420	2420
	Tricuspid Valve					
180	Procedure	OpTricus	-	4500	-	-
181	Tricuspid Valve Surgery	VSTV	3640	-	1650	1650
182	VAD implant type	VImpTy	-	4850	-	-
183	VAD implanted	VADImp	3840	-	2030	2030
184	VAD Implanted or	VADProc	2130	2480	-	-

Removed						
185	Valve Surgery	OpValve	2125	2440	1290	1290
186	VSD repair	OCarVSD	4155	5230	2370	2370
187 N. Other Non-Cardiac Procedures						
188	Carotid endarterectomy	ONCCarEn	4530	5560	2570	2570
189 P. Postoperative Events						
190	Postop stroke	CNSTrokP	4810	6030	2630	2630
191	Postop TIA	CNSTrokTTIA	4815	6040	2840	2840
192	Atrial Fibrillation	COAtFib	4930	6330	2990	2990
193	Reop for bleeding	COpReBld	4755	5760	2720	2720
	Postop pacemaker					
194	insertion	CRhythmDis	4900	6270	-	-
195 Q. Mortality						
196	Mortality	Mortality	5005	6360	3020	3020
197	Date of Death	MtDate	5030	6400	3060	3060
198	Primary cause of death	MtCause	5040	6420	3080	3080
199 R. Discharge (with Section S)						
200	Aspirin	DCASA	5060	6460	3120	3120
201	Warfarin	DCCoum	5085	6510	3180	3180
202	Antiarrhythmic	DCArhy	-	6440	3100	3100
203	Antiarrhythmic name	DCArMN	-	-	3110	3110
204	Readmission	Readm30	-	6550	3220	3220
	Primary readmission					
205	reason	ReadmRsn	-	6560	3230	3230
206	Amiodarone	DCAmiodarone	5110	-	-	-
207	Beta-blocker	DCBeta	5105	6480	3140	3140
208	Discharge location	DisLoctn	5045	6520	3190	3190

